1.14. Bronchoscopy

Bronchoscopies will be performed in the endoscopy suite at St Mary's Hospital, or at Hammersmith hospital, in accordance with BTS guidelines. During the confinement period, private transport from the confinement facility to the endoscopy suite will be mandatory. Subjects will be instructed to wear face masks during this visit, and staff will use appropriate personal protective equipment (PPE).

- Subjects will sign a consent form prior to being screened for the study and will **sign a separate consent form for each bronchoscopy**. The procedure will be explained during the assessment stage and **subjects will be given written information specifically regarding bronchoscopies in addition to the Participant Information Sheet**
- Subjects will fast for four hours prior to the procedure
- Resuscitation equipment (for intubation, ECG monitoring and defibrillation) and necessary drugs (salbutamol, theophylline, adrenaline, hydrocortisone) will be available in the bronchoscopy room
- Premedication may be given including:
 - Nebulised salbutamol 2.5mg 10-15 minutes prior to bronchoscopy
 - Sedation – midazolam (2-10mg) or fentanyl (50-100µg) as necessary
 - Lignocaine – gel and solutions (1-4%) for topical anaesthesia. The total dose will not exceed 400mg
- Supplemental oxygen at a rate of 2Lmin⁻¹ is given via a nasal cannula and oxygen saturations and heart rate are monitored with a pulse oximeter continuously. Intravenous access will be mandatory in all cases
- The subject will be monitored during the bronchoscopy by adequately trained clinical staff, according to Research Bronchoscopy SOP (V3).
- The following samples are collected in this order: (i) Bronchosorption using Synthetic Absorptive Matrix (SAM) (ii) Bronchial Brushings (iii) Bronchial Biopsy (iv) Bronchoalveolar lavage (BAL)
- All adverse events – pain, bleeding, hypoxia etc will be recorded and reported according to Section 8 of this protocol
- Subjects will be observed for a minimum of 2 hours and nil by mouth until safe
- Transportation will be arranged as subjects should not drive on the day of the procedure
- All subjects will have a contact telephone number on discharge

1.14.1. Bronchosorption:

‘Bronchosorption™ FX·i is a non-sterile, single-use device consisting of a synthetic absorptive matrix (SAM™) strip enclosed within a catheter for bronchial sampling. Bronchosorption™ FX·i is designed to operate through a flexible video bronchoscope with a maximum working length of 815mm. The SAM™ strip is 1.0mm wide, designed to work with a minimum instrument channel diameter of 2.0mm.’ Hunt Developments UK (Ltd).

- The device will be passed down the bronchoscope.
- The probe will be deployed for up to 120 seconds in segmental and larger bronchi to allow the SAM to absorb local epithelial lining fluid (ELF).
- The probe will then be resheathed and removed via the operating port of the bronchoscope.
- This will be repeated up to 4 times with a new device.
- The SAM will be transferred to polypropylene tubes for transport on ice to the laboratory and stored at -80 degrees C until analysis.

1.14.2. BronchoBronchial Biopsies:

Six bronchial biopsies will be taken from the segmental and sub-segmental bronchi of the right lower and middle lobe (RLL, ML). This is performed using *Keymed* 2mm biopsy channel cupped and fenestrated biopsy forceps [FB-19C-1 (1111065)]; four biopsies will be placed in 4% paraformaldehyde and stored in paraffin blocks and two placed immediately into RNeasy[®] (Qiagen) stabilisation solution and refrigerated for 24 hours prior to freezing at -80°C.

1.14.3. Bronchial Brushings:

Four bronchial brushings will be taken from the left lower lobe (LLL) sub-segmental bronchi with a standard cytology brush. The brush is washed in a tube containing RNA Cell Protect[®] (Qiagen) to preserve cells prior to freezing at -80°C. A new brush is used each time the brushes are washed and discarded.

1.14.4. Bronchoalveolar Lavage (BAL):

- BAL is performed by instillation of sterile physiological (0.9%) saline at room temperature into the left upper lobe (LUL) bronchus in 30ml aliquots to a total of 180-240ml
- Aiming for 80% volume recovery and aspirating after each instillation
- The BAL fluid is collected into a plastic chamber and transferred to polypropylene tubes for transport on ice to the laboratory
- BAL processing - Keep BAL collected at bronchoscopy on ice at all times

1.15. Blood sampling

Screening visit blood will be taken for full blood count, renal function, liver function tests, glucose, clotting, CRP, lymphocytes, immunoglobulins, HIV, hepatitis B and C. These will be processed in the Haematology and Chemical Pathology Laboratories of Imperial College Healthcare NHS Trust. Serology will be performed at screening and day -14 by IgG microneutralisation assay.

The total amount of blood taken at screening would amount to 40mL. Blood for peripheral blood mononuclear cells (PBMCs) will also be taken at day -14, 0, 3, 7, 14, 28, 161, 168, 175 and 196. On these occasions, 20-60mls of blood will be taken (see Table 1 & 2). In addition, during the first challenge, blood for gene expression profiling, serum and plasma will be taken from day 0 to day 10 plus day 14 and 28. Blood for gene expression profiling will be taken once or twice day. A maximum of 72 mls of blood will be taken on any single day for a total of 478.5 mls over the 28-day challenge period (see Tables 1 & 2).

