1.9. Withdrawal criteria

Any subjects can withdraw from the study at any time if they wish to. Subjects can also be removed from the study if an investigator feels this is necessary or appropriate. Subjects will be closely monitored throughout by the study doctor. This is defined further in the section on 'Serious Adverse Events'.

STUDY DESIGN**Figure 1: Subject allocation**
Day 0**Table 1: Study procedures (Screening to day 9)**

Procedures	DAY (relative to viral inoculation)												
	Screen	-14	0	1	2	3	4	5	6	7	8	9	
Consent	X												
Physical Examination	X	X	X							X			
Lung Function Testing – FEV ₁ , peak flow & breath tests	X	X	X	X	X	X	X	X	X	X	X	X	X
Screening blood tests	40												
Blood - serum			5										
Blood for HLA typing	5												
Blood - PBMCs (mls)			40										
Blood – plasma (mls)		X	6 x 2	6 x 2	6 x 2	6 x 2	6 x 2	6 x 2	6 x 2	6 x 2	6	6	
Blood – RNA (mls)			7.5 x 2	7.5 x 2	7.5 x 2	7.5 x 2	7.5 x 2	7.5 x 2	7.5 x 2	7.5 x 2	7.5	7.5	
Throat & stool swabs	X	X		X	X	X	X	X	X	X	X	X	X
Nasal lavage (daily)	X	X	X	X	X	X	X	X	X	X	X	X	X
Nasosorption using SAM (right nostril)	X	X		X	X	X	X	X	X	X	X	X	X
Nasal scrape (Rhinopro®)	X	X		X	X	X				X			
Bronchoscopy: Bronchosorption using SAM (4) Bronchial biopsy (6) Bronchial brush (4) Bronchoalveolar lavage (BAL)		X											
Virus inoculation			X										
Review symptom diaries daily	X	X	X	X	X	X	X	X	X	X	X	X	X
Collect symptom diaries													
Urine pregnancy test	X		X										

Table 2: Study procedures (day 10 to day 196)

Procedures	DAY (relative to viral inoculation)							
	10	14	28	161	168	178	182	196
Consent				X				
Physical Examination	X	X	X	X	X	X	X	X
Lung Function Testing – FEV ₁ , peak flow & breath tests	X	X	X	X	X	X		
Screening blood tests								
Blood - serum			5		5		5	5
Blood for HLA typing								
Blood - PBMCs (mls)	60		40	20	40	60	60	60
Blood – plasma (mls)	6	6	6					
Blood – RNA (mls)	7.5	7.5	7.5	7.5	7.5	7.5	7.5	7.5
Throat & stool swabs	X	X	X		X	X	X	X
Nasal lavage (daily)	X	X	X	X		X		
Nasosorption using SAM (right nostril)	X	X	X		X	X	X	X
Nasal scrape (Rhinopro®)	X				X	X	X	X
Bronchoscopy: Bronchosorption using SAM (4) Bronchial biopsy (6) Bronchial brush (4) Bronchoalveolar lavage (BAL)	X		X				X	
Virus inoculation					X			
Review symptom diaries daily	X	X			X	X	X	X
Collect symptom diaries		X					X	
Urine pregnancy test			X	X				

SAM = synthetic absorptive matrix

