On the morning of viral challenge, participants will attend the ICRRU or ICRF. A single nasal lavage sample will be taken to exclude coincident infection and blood will be taken for PBMCs. Following this, subject to a satisfactory assessment by the study doctor (brief interview and medical examination), we will infect the volunteers with RSV using a dose of 4 log PFU or with influenza at a dose of 3.5×10^6 TCID₅₀. After infection, participants will be observed for a period of 30 minutes to ensure no adverse reactions have occurred. They will enter a residential research facility (confinement facility), where they will reside for the next 8-10 nights so we can monitor the development of cold symptoms and collect samples to evaluate immune responses and test the hypotheses. These will include daily blood samples, throat swabs, nasal lavage, nasal SAM, nasal scrapes, lung function tests, as well as bronchoscopy on day 7 or 10 post-infection. Participants will be seen daily by the study team. On the 8th day of residence, assuming all significant symptoms have resolved and at the discretion of the principle investigator, participants will leave the confinement facility and asked to return daily for assessment and sampling. If symptoms continue or the study doctors deems it necessary, the volunteer will be asked to remain until the 9th or 10th day of residence at which time they will be discharged, subject to a satisfactory assessment by the study doctor. If a subject is discharged before the 10th day or wishes to withdraw after virus inoculation but before the 10th day, we will strongly advise them to confine themselves in their own homes, and to strictly avoid any contact with young children, the elderly or other high-risk individuals for the remainder of the period during which viral shedding may occur. Additionally, subjects infected with influenza withdrawing before the 8th day post-inoculation will be treated with oseltamivir to prevent reduce the risk of viral shedding having left confinement.

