Based on pilot data from de Bree et al., we calculate that a sample size of 16 in each arm will be sufficient to find a difference of 1.4 between epitope-specific T cell counts in blood and lung, with 80% power using a 2-sided unpaired t-test with 5% significance level (where the variability in each group is 1.3). T cell numbers will be compared between RSV and influenza using an unpaired t-test (if normality of the T cell distribution, or its transformation, is satisfactory as assessed by histogram with q-qplot and Shapiro-Wilks test) or a Mann-Whitney test (if normality is not satisfactory). We will perform microarray analysis on each of 6 patients prior to inoculation and at 3 post-baseline timepoints. Our main analysis will identify differentially expressed genes between influenza and RSV at each post-baseline timepoint. The sample size, calculated using the size package from bioconductor which provides pilot data of gene expression variability from the U95 package, predicts that 6 individuals in each group will give us 80% power to detect a potential fold change of 3 in up to 67% of the genes with a Bonferroni multiple testing correction with a genome-wide 5% significance level.

Quantitative assessments of symptom scores, lung function, virus load, leukocyte numbers and inflammatory markers will be compared within subjects to determine differences between baseline and during infection. Intra-subject differences will be analysed using ANOVA and 2-tailed paired Student's t-tests or Wilcoxon signed rank test as appropriate. Correlations between inflammatory cell, illness severity, viral load and leukocyte counts will be examined using Spearman's rank correlations to investigate possible causal relationships.

Data and all appropriate documentation will be stored for a minimum of 10 years after the completion of the study, including the follow-up period according to Imperial College London policy.

REGULATORY ISSUES

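### Section 1.15 and Tables 1-2 give incompatible PBMC draw days, no day is named for the primary T-cell comparison, and the stated 72 mL daily blood maximum is exceeded on day 10

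*Combined protocol and SAP*

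**What the plan says.** Section 1.15 states that blood for PBMCs "will also be taken at day -14, 0, 3, 7, 14, 28, 161, 168, 175 and 196". It continues: "On these occasions, 20-60mls of blood will be taken (see Table 1 & 2", so it presents the Tables as the source of the volumes. It then gives the limits: "A maximum of 72 mls of blood will be taken on any single day for a total of 478.5 mls", with the total attributed to the 28-day challenge period.

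The PBMC row of Table 1 has a single entry, 40 mL on day 0. The PBMC row of Table 2 has entries of 60, 40, 20, 40, 60, 60 and 60 mL on days 10, 28, 161, 168, 178, 182 and 196. Day 14 is blank.

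Other sections bear on the same schedule:

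- Section 1.10.1 includes PBMCs in the baseline visit (day -14).
- Section 1.10.2 lists the confinement samples "as well as bronchoscopy on day 7 or 10 post-infection". Table 2 marks bronchoscopy on day 10.
- Section 1.10.3 places a sample 7 days after the second RSV inoculation, which is given in the RSV arm only.
- The Statistics and Data Analysis section compares T-cell numbers between RSV and influenza without naming a day. It plans microarrays "on each of 6 patients prior to inoculation and at 3 post-baseline timepoints", naming neither the days nor the specimen.
- The Assessment and Follow-up section ends the influenza arm at day 28 and the RSV arm at day 196.

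**The concern.** The primary objective is a comparison of T-cell responses between RSV and influenza, and PBMCs are the blood material for it. A site cannot follow both schedules as written, and cells not drawn on a given day cannot be recovered later. If staff work from different parts of the protocol, the acute-phase sample may come from different days. With no day named in the statistics section, the choice of day for the primary test is left open until after the data exist.

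The blood-volume sentence is a limit set for healthy volunteers. A plan that exceeds its own limit, even slightly, needs correcting.

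**Working it through.** **1. PBMC days side by side**

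| Period | Section 1.15 | Tables 1-2 | In both |
|---|---|---|---|
| Before challenge | -14, 0 | 0 | 0 |
| First challenge, post-inoculation (both arms) | 3, 7, 14, 28 | 10, 28 | 28 |
| Around and after second challenge (RSV only) | 161, 168, 175, 196 | 161, 168, 178, 182, 196 | 161, 168, 196 |

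The text's day -14 agrees with section 1.10.1. Its day 175 agrees with section 1.10.3, since 168 + 7 = 175. The Tables have no day-175 column.

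**2. Is this a misread table?** The day-0 and total volumes, summed from the table cells as read, test this. Inputs are the serum, PBMC, plasma and RNA rows, in mL:

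- Day 0: 5 + 40 + (6 x 2) + (7.5 x 2) = 72
- Days 1-7: 12 + 15 = 27 each; 7 x 27 = 189
- Days 8-9: 6 + 7.5 = 13.5 each; 2 x 13.5 = 27
- Day 10: 60 + 6 + 7.5 = 73.5
- Day 14: 6 + 7.5 = 13.5
- Day 28: 5 + 40 + 6 + 7.5 = 58.5
- Days 0-28: 72 + 189 + 27 + 73.5 + 13.5 + 58.5 = 433.5
- With screening (40) and HLA typing (5): 433.5 + 45 = 478.5

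The plan's 72 mL is the day-0 sum, and its 478.5 mL is reproduced exactly. A misread table is therefore an unlikely explanation for the conflict within days 0-28.

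**3. The daily maximum.** Day 10 is 73.5 mL, 1.5 mL above 72. Days 182 and 196 are each 5 + 60 + 7.5 = 72.5 mL, 0.5 mL above it if the limit also covers the second challenge.

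**4. The volumes on the section 1.15 days.** Assume that days 0 and 28 keep 40 mL, that the day-10 draw of 60 mL is removed, and that days -14, 3, 7 and 14 each take between 20 and 60 mL:

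- Total with screening: 478.5 - 60 + 4 x 20 = 498.5, up to 478.5 - 60 + 4 x 60 = 658.5
- Total without screening: 453.5 to 613.5
- Days 3 and 7: 27 + 20 = 47, up to 27 + 60 = 87

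Counted as the Tables total is counted, with screening, 478.5 mL cannot hold on the section 1.15 days. Without screening it lies inside the range, but the volumes for these days are not stated.

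**5. Arrays.** The RNA row gives 12 post-baseline days up to day 28 (days 1-10, 14 and 28). If the arrays instead use T cells separated from PBMCs, the Tables give two post-baseline days shared by both arms (10 and 28) against three planned. Section 1.15 would give four (3, 7, 14 and 28).

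**The case against.** Several stronger readings are tempting, and the documents do not support them.

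- *A reader might infer that the three planned arrays cannot be done on the Tables.* The separate RNA row and the gene-expression sampling in section 1.15 give ample days. The shortfall exists only if the arrays need T cells separated from PBMCs. The secondary objective, which concerns T-cell transcription, suggests that; the statistics section does not say it.
- *A reader might infer that the primary day is undetermined because the draw days conflict.* The main cause is that the statistics section names no day. That would remain so if the schedules agreed, and day 28 is available on both.
- *A reader might count every mismatched day against the primary comparison.* Days 175, 178 and 182 follow the RSV-only second inoculation and cannot affect it, and day -14 precedes challenge. What matters there is 3, 7 and 14 against 10.
- *A reader might infer bias between arms or an inflated error rate.* No section assigns different days by virus. Four tests at 5% would give 1 - 0.95^4 = 18.5%, but only if independent. The plan does not set out those tests, and counts from the same people would be correlated.
- *A reader might call the 478.5 mL total wrong.* It reproduces once screening blood is included; its label is what does not fit.

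It is also fair to say that day 7 or 10 for bronchoscopy includes the Table's day 10, so it is an unresolved option more than a contradiction, and that 1.5 mL is about 2% of the limit. All of this narrows the point. It does not remove the conflict in PBMC days, the missing primary day or the exceeded maximum.

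**Conclusion.** The point holds in this limited form. Section 1.15 and Tables 1-2 cannot both be followed. In the window the two arms share, only day 28 of the post-challenge PBMC days agrees; in the RSV-only second challenge, day 175 stands against days 178 and 182. Separately, the primary T-cell comparison has no named day. The 72 mL maximum is wrong on the Tables by 1.5 mL on day 10, and by 0.5 mL on days 182 and 196 if they fall under it. The 478.5 mL total is right with 45 mL of screening and HLA blood, but it is labelled as the 28-day period, for which the Tables give 433.5 mL.

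These sums rest on the table cells as read and leave out the plasma draw apparently marked at day -14, which has no stated volume. The figures for the section 1.15 days rest on the assumed 20-60 mL per draw. The documents do not settle which schedule is intended.

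**What to change.** 1. Reconcile sections 1.10.1, 1.10.2, 1.10.3 and 1.15 and Tables 1-2 to one list of PBMC and bronchoscopy days.
2. In the statistics section, name one post-challenge day, the same in both arms, for the primary T-cell comparison. Make other days secondary.
3. State the array specimen and the three post-baseline days, and check that they fit the reconciled list in both arms.
4. Recompute the daily maximum and total from that list, saying whether screening blood is counted and giving a volume for the day -14 plasma draw. On the current Tables, without that draw, the figures are 73.5 mL and 433.5 mL, or 478.5 mL with screening.
5. In the same pass, align the serum days: section 1.15 reads as serum on days 0-10, 14 and 28, while the Tables show it in that period only on days 0 and 28.

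The cost is a protocol amendment and a slightly less favourable daily blood figure. Any draw days added to the Tables mean more blood from each volunteer. No extra participants are needed.

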1.16. Physical examination

Physical examination, including ENT, respiratory and cardiac assessment will be performed by the study doctor at screening and days -14, 0 (prior to inoculation), 8, 9, 10, 14, 28 and 175 days post inoculation.

1.17. Lung Function Tests

Predicted Values for Lung Function Measurements: the predicted or reference values for lung function measurements are those recommended by the Report Working Party for the European Community for Coal and Steel. Also incorporated are the recommendations of the British Thoracic Society and the Association of Respiratory Technicians and Physiologists.

1.17.1. Measuring FEV₁ and FVC by Spirometry

Performing the measurement

- Posture must be consistent during a study, either standing or sitting, with no breathing limitation
- The subject should breathe in to total lung capacity. A good tight seal by the lips round the mouthpiece is essential. The subject should then exhale forcibly into the spirometer, blowing as hard as possible and continue to residual volume
- The best value of 3 attempts will be recorded

Calibration: Diagnostic spirometers will be serviced and calibrated by the relevant company for the brand. However, the calibration will be checked at least once a month using a calibrated one litre syringe.

At the screening visit and at other visits as described in the table in, measurements of FEV₁ and FVC will be made as outlined above.

1.17.2. Collection and analysis of exhaled breath

Exhaled breath is believed to contain infectious virus during natural influenza infections. To collect potentially infectious particles in breath exhaled during infection, we will use an altered resuscitation mask with Teflon filter mouthpiece into which the participant will be asked to breath for 20 minutes.

1. The test will take a total of thirty minutes including twenty minutes of quiet breathing.
2. A study team member will explain what the device consists of and why the test is being performed.
3. The participant will hold the mask by the cardboard tubing and not touch any plastic surface.
4. They will gently press the mask against their face, covering the mouth and nose.
5. Then they test breathing through their nose and mouth while study staff check for leaks around the face.
6. If the participant experiences pinching of their nose, difficulty in nasal breathing or a leak is detected air can be removed with a 20 ml catheter tip syringe from the inflatable cuff on the facemask and the mask re-tested.
7. Once steps 4 and 5 have been optimised the participant will be asked to breath in through their mouth and out through their nose (normal tidal volumes and rate).
8. If their nose is blocked due to symptomatic infection mouth breathing will be performed and this will be documented in the Breath Collection Log.
9. The participant will be asked not to speak, unless it is necessary.
10. They will be asked not to remove the mask from their face, unless absolutely necessary.
11. It will be explained that if the seal around their face is broken, e.g. if they remove the mask, the test will be restarted.

1.18. Clinical symptom scores

A self-completed diary card of both upper and lower respiratory tract clinical symptoms will be made at baseline 14 days prior to inoculation (prior to nasal washing and / or bronchoscopy), on day 0, and daily for 14 days.

Additionally, the symptom diary will be completed daily for 7 days after the 1st bronchoscopy (i.e. day -14 to day -7). This is to allow the effect of bronchoscopy on symptoms to be measured and adjusted.

Individual symptom scores will be accumulated over the six-day period of maximal illness (days 2-7) after inoculation and the baseline recording (including any effect measured from the 1st bronchoscopy where appropriate) subtracted from the post inoculation recordings. Thus, for a patient who has a score of zero on day 0 prior to inoculation, the maximum cumulative score for the following six days is 144.

Upper Respiratory Tract Symptoms

A total 'upper respiratory clinical symptom score' will be derived using a four-point scale (0-3 for absent, mild, moderate and severe) for each of the following eight respiratory symptoms: sneezing, headache, malaise, fever/chills, nasal discharge, nasal obstruction, sore throat and cough according to established methods, giving a maximum clinical severity score of 24. This is an established method for studies of common cold illnesses⁴⁴. Symptoms will be recorded at the same time of day and before any procedures such as bronchoscopy or nasal lavage are performed.

An example is shown below:

Symptom	Day 1	Day 2	Day 3	Day 4	Day 5	Day 6	Day 7
Sneezing							
Headache							
Malaise							
Fever / chills							
Nasal discharge							
Nasal obstruction							
Sore throat							
Cough							
Total score							

0 = absent, 1 = mild, 2 = moderate, 3 = severe

Definition of a clinical cold

A clinical cold is diagnosed if **two or more** of the following are present:

- A cumulative clinical symptom score of 14 or greater over a 6 day period
- Nasal discharge is present on three or more days over the six-day period post viral inoculation
- A subjective impression of a cold developing. This latter criterion is used because there are a few subjects who have had a very strong subjective impression of a clinical cold but the cumulative clinical score does not reach the arbitrary cut-off level

System, Lower Respiratory Tract and Other Symptoms

A diary card of lower respiratory tract symptoms will be completed with a scoring system outlined below.

SYMPTOM	Day 1	Day 2	Day 3	Day 4	Day 5	Day 6	Day 7
Cough							
Difficulty breathing							
Hoarseness							
Chest discomfort							
Chills							
Diarrhoea							
Muscle aches							
Feeling/being sick							
Red/watery eyes							
Wheezy chest							
TOTAL SCORE							

Absent = 0 Mild = 1 Moderate = 2 Severe = 3

ADVERSE EVENTS

